8.1.3. Primary efficacy analysis

Logrank test is used for the analysis of relapse-free survival rate which is then used as a covariate for stratification by Sites. HR and its 95% confidence interval (CI) are calculated with Cox proportional hazard model to estimate the efficacy, the confidence interval is applied to verify the superiority of the experimental group and the control group, with a cut-off value of 1 (risk ratio). The model incorporates the same covariate as the Logrank test for fitting, and the definition method of covariates is also the same as that in the Logrank test. The Kaplan-Meier curve of relapse-free survival is drawn by treatment groups. The 1-year relapse-free survival rate and its confidence interval are then calculated.

Calculation rules for the main efficacy indicators:

- If relapse occurred within 9 visits (within 364 ± 7 days) or unscheduled visits within 365 days of randomization, defined as the occurrence of endpoint events. Time of relapse = date of relapse - Random date + 1, calculated by days.
- If the visit stipulated in the protocol was not completed within 9 visits (within 364 ± 7 days) due to loss of follow-up midway or withdrawal or other reasons, it is defined as censoring. Time of

censoring = date of withdrawal - random date + 1, calculated by days.

- If the visit stipulated in the protocol was not completed within 9 visits (within 364 ± 7 days) due to death in the trial, it is defined as censoring. Time of censoring = Death date - random date + 1, calculated by days.
- If the visit stipulated in the protocol was completed and there is no relapse within 9 visits (within 364 ± 7 days), it is defined as censoring. Time of censoring = date of visit 9 (within 364 ± 7 days) - random date + 1, calculated by days.

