4.2.2 Determination of the number of cases

It is estimated that 1-year relapse-free survival is 0.56 in MMF Group, and 0.70 in FK506 Group. The enrollment time of this research is expected to be 2 years, and the total time of this research is 3 years, with a test level $\alpha = 0.05$, and a power of test $1 - \beta = 80\%$. It is estimated to have 114 patients in MMF group and 115 patients in FK506 group, with a total of 229 patients. With the consideration of 15% loss of follow-up, a total of 270 patients are needed, including 135 patients in each group.

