4.5.3. Elimination criteria

- Those who fail to take the test drugs as required, with a compliance <80% or >120%.
- Those who cannot cooperate well or complete the follow-up as planned, and those who change the drug dose at will.

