7.1. Analysis data set

Full analysis set (FAS): It refers to the set of eligible cases and drop-off cases. The cases are required to have evaluation data after at least one treatment, but excluding the eliminated cases. Per-protocol set (PPS): It refers to the set of cases that meet the inclusion criteria, do not meet the exclusion criteria and complete the treatment plan, that is, the analysis of cases that meet the trial protocol, have good compliance and complete the specified content in CRF (PP analysis).

Safety set (SS): It refers to the actual data with safety index records after receipt of at least one treatment. The missed safety values shall not be carried forward. It includes some eliminated cases that can be evaluated, such as those whose age exceeds the inclusion criteria, but excludes those whose safety judgment cannot be made due to the use of banned drugs. For the incidence of adverse reactions, the number of cases in the safety set is used as the denominator.

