9.1. Research overview

Table 1. Distribution of subjects at each site (All enrolled subjects)

Research Site	Group	No. of subjects enrolled	No. of subjects drop-out	Drop-out rate	No. of subjects eliminated	Elimination rate	No. of subjects completed
Site 1	Experimental group						
	Control group						
	Total						
Site 2	Experimental group						
	Control group						
	Total						
...							
Total	Experimental group						
	Control group						
	Total						

Note: 1. The Site name is not displayed in following table, only the site number. Same below. 2. No. of subjects completed = No. of subjects enrolled - No. of subjects drop-out. Elimination refers to subjects who complete the trial, but were not included in the PPS. Subjects who withdrew due to the endpoint event were considered to have completed the trial. 3. Drop-out rate = No. of subjects drop-out / No. of subjects enrolled; Elimination rate = No. of subjects eliminated / No. of subjects enrolled.

Table 2. Distribution of subjects at each site

Site	PPS			FAS			SS		
	Experimental group	Control group	Total	Experimental group	Control group	Total	Experimental group	Control group	Total
Site 1									
Site 2									
Total									

Table 3. Trial completion and distribution of analysis data set (All enrolled subjects)

Items	Indicator	Experimental group	Control group	Total
No. of subjects enrolled	Yes			
	No			
Complete 1 week follow-up	Yes			
	No			
Complete 4 week follow-up	Yes			
	No			
Complete 8 week follow-up	Yes			
	No			
Complete 16 week follow-up	Yes			
	No			
Complete 24 week follow-up	Yes			
	No			
Complete 32 week follow-up	Yes			
	No			
Complete 40 week follow-up	Yes			
	No			
Complete 52 week follow-up	Yes			
	No			
Trial completion	Yes			

Items	Indicator	Experimental group	Control group	Total
	No			
Treatment discontinuation reason	Subject voluntarily withdrew prematurely			
	Decision by the investigator			
	Poor compliance that decided by the investigator			
	Meet the exclusion criteria, or did not meet the inclusion criteria			
	Refusal to continue trial participation			
	Lack of efficacy			
	Adverse events			
	Lost to follow-up			
	Death			
	Other			
FAS				
PPS				
SS				

Note: Follow-up time (years) = (last visit date - random date + 1) / 365.25. Complete 1 week follow-up: follow-up duration \geq 1 week, and so on.

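### Early exits are censored at the withdrawal date instead of the last date relapse status was known, and two conflicting definitions of elimination leave unclear whether non-completers stay in the full analysis set

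*SAP*

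**What the plan says.** **Event.** SAP 8.1.3 counts a relapse within the visit 9 window, or at "unscheduled visits within 365 days of randomization, defined as the occurrence of endpoint events".

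**Exit.** A child who does not complete the visits "due to loss of follow-up midway or withdrawal or other reasons, it is defined as censoring". The time is dated by the rule "censoring = date of withdrawal - random date + 1, calculated by days". Non-completion "due to death in the trial, it is defined as censoring" as well, at the death date. Protocol 11.3.3 has no counterpart to these rules. SAP section 8 (missing data) says survival data need no filling.

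**Analysis set.** SAP 7.1 puts eligible and drop-off cases in the FAS and then adds: "The cases are required to have evaluation data after at least one treatment, but excluding the eliminated cases".

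**Elimination, defined twice.** SAP 4.5.3 lists "Those who cannot cooperate well or complete the follow-up as planned". The note under Table 1 (SAP 9.1) says: "Elimination refers to subjects who complete the trial, but were not included in the PPS". The same note treats a child who withdraws because of the endpoint event as having completed.

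**Other relevant text.** SAP 8.1.2 bases efficacy on ITT principles and asks investigators to report all potential endpoint events. SAP 4.5.5.2 keeps drop-out data for analysis. SAP 8.1.5, Table 3 and Table 109 compare, tabulate and list the exits. The only loss figure is in SAP 4.2.2: "With the consideration of 15% loss of follow-up, a total of 270 patients are needed".

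**The concern.** Log-rank, Cox and Kaplan-Meier methods need two things from a censored child: that the child was known to be relapse-free up to the censoring date, and that the later risk matches that of children still followed.

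The first fails if a silent loss is dated at an administrative withdrawal weeks after the last relapse assessment. The added time counts as relapse-free without evidence, which pushes the rates up.

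The second may fail because some listed exit reasons could relate to relapse risk: aggravated condition, lack of efficacy, a prohibited immunosuppressant, target level not reached. No planned output shows how far this would move the rates or the hazard ratio. The per-protocol set requires completion of the treatment plan, so it tends to leave exits out and does not test how they are handled.

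Before either question arises, the exit must be in the analysis. If SAP 4.5.3 governs the FAS, a non-completer is removed altogether and the censoring rule never applies.

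**Working it through.** **1. The plan's own figures.** Relapse-free 0.56 (MMF) and 0.70 (FK506) give hazards λ = −ln 0.56 = 0.580 and −ln 0.70 = 0.357 per year, HR 0.357/0.580 = 0.615. A Lakatos log-rank calculation with 114/115 children, accrual 2 of 3 years and no loss gives power 0.7998 and 133.7 events (stated: 0.8009 and 133.8). Then 229/0.85 = 269.4, rounded up to 270. The steps below follow each child for one year, as SAP 4.1 describes, so event counts are lower than 133.8.

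**2. Expected exits (assumption: 15% loss in each arm at a constant rate).** μ = −ln 0.85 = 0.1625. With 135 per arm, person-years = 135 × [1 − e^−(λ+μ)]/(λ+μ), events = λ × person-years, exits before relapse = μ × person-years.

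| | MMF | FK506 |
|---|---|---|
| Person-years | 95.3 | 105.3 |
| Relapses | 55.3 | 37.6 |
| Exits before relapse | 15.5 | 17.1 |

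**3. Late dating.** The flow chart puts visits 4 to 9 at days 56, 112, 168, 224, 280 and 364, so the gaps are 56, 56, 56, 56 and 84 days. If each exit is dated d days late, exits add μ × person-years × d/365, and the estimated hazard becomes λ/(1 + μd/365).

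| d (days) | MMF rate | FK506 rate | Rise (points) | HR |
|---|---|---|---|---|
| 28 | 0.564 | 0.703 | 0.4 / 0.3 | 0.615 |
| 42 | 0.566 | 0.705 | 0.6 / 0.5 | 0.615 |
| 56 | 0.568 | 0.706 | 0.8 / 0.6 | 0.615 |
| 84 | 0.572 | 0.709 | 1.2 / 0.9 | 0.615 |

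The divisor is the same in both arms when μ is, so it cancels from the HR. If exits were 10%/20% (assumed; μ = 0.105 and 0.223), 84 days would give 0.615 × 1.024/1.051 = 0.60, and the reverse split 0.63. The 56- and 84-day rows are high-side figures: they date every exit a full interval late, while visits up to day 56 are 28 days apart or less.

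**4. Higher risk after exit (assumption: hazard k times the arm's own).** Full-follow-up rate = e^−(λ+μ) + ∫₀¹ μ e^−(μ+λ)u e^−kλ(1−u) du; HR from the Cox score equation.

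| Exits MMF/FK506 | k | True rates | Full-follow-up HR |
|---|---|---|---|
| 15%/15% | 1 | 0.560 / 0.700 | 0.615 |
| 15%/15% | 2 | 0.539 / 0.683 | 0.617 |
| 10%/20% | 2 | 0.546 / 0.677 | 0.643 |
| 20%/10% | 2 | 0.532 / 0.689 | 0.593 |

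The planned analysis would report 0.56/0.70 and 0.615 in every row. If all exits fall in months 1 to 6, the 15%/15% overstatement at k = 2 is 2.8/2.3 points with HR 0.618, and the unequal splits give 0.653 and 0.586.

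**5. Elimination.** Take a child who stops attending at month 5.
- SAP 4.5.5.1: a drop-out, so in the FAS under 7.1.
- SAP 4.5.3: did not complete follow-up, so eliminated and out of the FAS under 7.1.
- Table 1 note: not a completer, so not eliminated, and in the FAS.

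The child is both in and out. Only the last reading gives the censoring rule anything to act on.

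**The case against.** The case for leaving this alone is strong in several places.

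- **The hazard ratio barely moves on documented inputs.** The 15% figure comes with no split by arm. At equal loss and doubled hazard the change is 0.615 to 0.617–0.618. Even an assumed 10%/20% split at doubled hazard gave a simulated type I error of about 5.5% (unstratified log-rank, 6,000 runs). This stands.
- **Relapse-driven withdrawals are already events.** The Table 1 note expects them, and under SAP 5.2.2 relapse does not itself end study drug. Exits for lack of efficacy or aggravated condition may often follow a relapse that already counts. How many do not is unknown. This stands.
- **Relapses after exit.** A reader might infer that these are discarded. The documents lean the other way: bullet 1 of 8.1.3 does not require the child still to be enrolled, and 8.1.2 and 4.5.5.2 support counting them. A confirming sentence is all that is needed.
- **Imbalance would be visible.** SAP 8.1.5, Table 3 and Table 109 show it, though not its effect on the result.
- **A composite counting reason-based exits as events would not diagnose the problem.** If a third of 15% non-informative exits counted, its HR would be (0.357 + 0.054)/(0.580 + 0.054) = 0.648, a move with no bias present. It would also rest on clinician-judged reasons in an open-label trial.

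None of this answers the two points about stated rules: the censoring date, and the conflict over who is eliminated.

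**Conclusion.** The point holds for two stated rules.

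1. The withdrawal date is the wrong anchor when it falls after relapse status was last known. The size is small: about 0.6 to 1.2 points on the relapse-free rates if 15% leave and every loss is a full 56 to 84 days late, 0.3 to 0.6 at half an interval, and no change in the HR when exits are equal.
2. SAP 4.5.3, 7.1 and the Table 1 note cannot all apply. On one reading non-completers are deleted from an analysis described as ITT. The documents give no means of sizing this.

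The missing sensitivity analysis is a lesser matter. Doubled post-exit risk overstates the rates by about 2 points at 15% per arm with exits spread over the year, and the HR stays near 0.617. A reader might infer that the treatment comparison itself is unreliable. The documents do not support that: an HR of about 0.59 to 0.65 needs doubled risk and an assumed 10%/20% imbalance, and wider ranges need more extreme assumptions still. No size can be given for censoring deaths, because no death rate is stated. Exit rates by arm, exit timing and post-exit hazards are all assumptions here.

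**What to change.** 1. **SAP 8.1.3.** Censor at the last date relapse status was known. Add one sentence confirming that a relapse meeting the trial's criterion and documented within the bullet 1 window is an event in the assigned group even after withdrawal. Report by arm how many exits have known status to day 364, because selective contact could itself bias the result.
2. **SAP 4.5.3, 7.1 and the Table 1 note.** Settle on one definition of elimination under which non-completers stay in the FAS.
3. **Optional supplement.** Repeat the primary estimates with the post-exit relapse hazard varied by arm (equal, doubled, higher), shown beside exit counts by arm. Unlike a composite, this leaves the HR where it is when exits are non-informative.

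The primary event definition and the clinical withdrawal criteria stay unchanged.

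**Cost.** A few sentences, one reconciled definition, a line of counts and at most one extra table, all settled before database lock. SAP 4.1 describes enrollment as complete, and the drop-out contact in 4.5.5.2 does not expressly record relapse status, which needs three consecutive days of findings. Some status will therefore be unrecoverable, and those children are censored at last known status. Counting relapses after exit also brings some off-treatment time into the estimate, which fits the stated ITT principle.

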8.1.4. Secondary efficacy analysis

Secondary outcomes (renal function; cumulative steroid dosage; blood pressure; height; body weight; blood lipids; hemoglobin; serum albumin; urinary protein/creatinine (morning urine); 24hr urinary protein quantification (applicable to subjects > 3 years old); frequency of relapses; the time of the first relapse after enrollment; relapse-free rate in the first six months after enrollment) are described and compared with use of the above general Statistical methods, and the adverse reactions are analyzed by descriptive analysis.

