11.3.4 Secondary efficacy analysis

Secondary outcomes (renal function; cumulative steroid dosage; blood pressure; height; body weight; blood lipids; hemoglobin; serum albumin; urinary protein/creatinine (morning urine); 24hr urinary protein quantification (applicable to subjects > 3 years old); frequency of relapses; the time of the first relapse after enrollment; relapse-free rate in the first six months after enrollment) are described and compared with use of the above general statistical methods, and the adverse reactions are analyzed by descriptive analysis.

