6.2. Efficacy evaluation

6.2.1. Primary observation outcomes: 1-year relapse-free survival

6.2.2. Secondary observation outcomes:

- (1) Frequency of relapses; the time of the first relapse after enrollment; relapse-free survival in the first six months after enrollment;
- (2) Renal function: Serum creatinine and glomerular filtration rate (eGFR, see Appendix 1 for the calculation method)
- (3) Cumulative steroid dosage: The total amount of steroids taken during this research and the total amount of steroids in the first half of the year
- (4) Others: Blood pressure (see Appendix 2 for details), height, weight, blood lipid, hemoglobin, blood albumin, urinary protein/creatinine (morning urine), etc.
- (5) Adverse reaction
- (6) 24hr urinary protein quantification (applicable to subjects > 3 years old)

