7.2. General considerations of date analyses

7.2.1. General Statistical methods

SAS 9.4 software is adopted for Statistical analysis. Two-sided test is adopted for all Statistical tests. If the P value is less than 0.05, the tested difference will be considered "Statistically significant" (unless otherwise specified).

Descriptive analysis: Sort out and summarize a large number of data obtained from the survey to find out the internal law of these data - centralized trend and decentralized trend. Single factor analysis is mainly carried out with the help of statistics represented by various data, such as mean and percentage.

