7.2.2. Statistical inference method

- The description of quantitative indicators includes the calculation of the mean, standard deviation, median, minimum value, maximum value, lower quartile (Q1), upper quartile (Q3), as well as the number and percentage of various types of classification indicators.
- In the comparison of the general conditions between the two groups, appropriate methods shall be adopted for analysis according to the type of indicators. The group t-test or Wilcoxon rank sum test is used for the comparison of quantitative data between two groups; Chi-square test or exact probability method is used for classification data; Wilcoxon rank sum test or CMH test is used for hierarchical data.
- The report is mainly expressed in tables: The tables are self-evident, that is, they have table titles, table notes and number of cases.

8. Data handling conventions

Data conversion:

Age (years) = (date of signing of informed consent form - date of birth + 1) / 365.25, rounded down.

Drug-related definitions are: definitely related, probably related, and possibly related.

Missing date: Since it is survival analysis data, it does not need to be filled. Missing text-type data is displayed as "" in the list. Numeric data is missing from the list with "." to display. If the data is recorded as "not applicable"/"NA" and "unable to assess"/"NK", the data will be displayed as raw records when described in the inventory, and processed as missing data for Statistical analysis.

Outlier: In general, all assay results will be used for Statistical analysis. If there is a clear outlier caused by special reasons and affects the Statistical analysis, it is missing and marked in the

Statistical analysis results / report.

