9.4.2. Secondary efficacy indicators

9.4.2.1. The first relapse survival analysis after enrollment

Table 20. The time of the first relapse after enrollment

Items	Indicator	FAS		PPS	
		Experimental group	Control group	Experimental group	Control group
The time of the first relapse after enrollment (days)	N (Missing)				
	Mean (SD)				
	Median				
	Q1, Q3				
	Min, Max				
	95%CI				
	P-value				

Note: The time of first relapse after enrollment (days) = Date of first relapse after enrollment - Random date + 1.

Table 21. The first relapse survival analysis after enrollment

Items	Indicator	FAS		PPS	
		Experimental group	Control group	Experimental group	Control group
The time of the first relapse after enrollment (days)	N (Missing)				
	Endpoint event (%)(%)				
	Censoring (%)				
	Median survival time				
	95%CI				
	Q1, Q3				
	Log-rank test				
Cox regression analysis	Hazard Ratio				
	95%CI				
	Wald Chi-square				
	P-value				

9.4.2.2. 6-month relapse-free survival analysis after enrollment

Table 22. 6-month relapse-free survival analysis after enrollment

Items	Indicator	FAS		PPS	
		Experimental group	Control group	Experimental group	Control group
6-month recurrence time (days)	N (Missing)				
	Endpoint event (%)(%)				
	Censoring (%)				
	Median survival time				
	95%CI				
	Q1, Q3				
	Log-rank test				
Cox regression analysis	Hazard Ratio				
	95%CI				
	Wald Chi-square				
	P-value				

Figure 3. 6-month relapse-free survival analysis chart (FAS)

Figure 4. 6-month relapse-free survival analysis chart (PPS)

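### Secondary outcomes: Table 20 tests time to relapse among relapsers only, beside a log-rank/Cox result for the same outcome, and relapse frequency has no comparison table

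*SAP*

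**What the plan says.** SAP 8.1.4 lists the secondary efficacy outcomes and says they "are described and compared with use of the above general Statistical methods". Protocol 11.3.4 says the same ("are described and compared with use of the above general statistical methods"). In SAP 7.2.2 those methods come down to "appropriate methods shall be adopted for analysis according to the type of indicators", followed by a short list. For quantitative data: "The group t-test or Wilcoxon rank sum test is used for the comparison of quantitative data between two groups". For categorical data it gives chi-square or exact tests, and for ordered data Wilcoxon or CMH. None of these uses censoring or time observed.

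The table shells add detail:

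- **First relapse (SAP 9.4.2.1).** Table 20 has rows for N (Missing), mean, median, 95% CI and a P-value, with no test named. Its note defines the variable: "The time of first relapse after enrollment (days) = Date of first relapse after enrollment - Random date + 1". The next shell, "Table 21. The first relapse survival analysis after enrollment", gives events, censoring, log-rank and a Cox hazard ratio. Table 22 does the same at six months.
- **Relapse frequency.** SAP 6.2.2 names "Frequency of relapses; the time of the first relapse after enrollment" among the secondary outcomes. No table summarises or compares post-randomization relapse counts: Table 7 covers pre-enrollment history and Table 117 is a by-patient listing.
- **Steroids (SAP 9.4.2.4).** Tables 28-29 compare total amounts, with no unit and no scaling for weight.
- **Repeated measures.** Tables 23 and 67 are titled as covering each visit but go from Visit 2 (day 7) to Visit 4 (day 56). The flow chart schedules Visit 3 at day 28. The shells compare unadjusted changes from baseline.

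**The concern.** A child who does not relapse has no relapse date, so under its own definition Table 20 can only count that child as missing. Its P-value therefore compares two subgroups selected by a post-randomization event. It ignores how many children relapsed, which is where a treatment effect would mainly show. Table 21 uses every child and answers the intended question. The SAP prints both and does not say which governs, so a reader could take a non-significant Table 20 as evidence against an effect that Table 21 shows.

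The remaining gaps are smaller. Relapse frequency, steroid use and renal function are the secondary results on which these two drugs would be weighed. The trial is open-label, so methods left open until data are seen invite doubt.

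**Working it through.** **Reproducing the plan's figure.** Inputs from SAP 4.2.2 and Protocol Appendix 4: one-year relapse-free survival 0.56 (MMF) and 0.70 (tacrolimus), accrual 2 of 3 years, 114 + 115 patients.

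- Exponential hazards: −ln 0.56 = 0.5798 and −ln 0.70 = 0.3567 per year; HR = 0.3567/0.5798 = 0.615.
- Events = n × [1 − (e^(−λ) − e^(−3λ))/(2λ)]: 114 × 0.6685 = 76.2 and 115 × 0.4995 = 57.4, total 133.7 (plan: 133.8).
- Schoenfeld power at 133.8 events: Φ(√133.8 × 0.4859/2 − 1.96) = 0.80 (plan: 0.8009). 229/0.85 rounds up to 270.

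**(a) Table 20 against Table 21**, with 135 per arm observed for one year.

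- Relapsers: 135 × 0.44 = 59.4 and 135 × 0.30 = 40.5. The other 270 − 99.9 = 170.1 children (63%) have no Table 20 value.
- Mean time among relapsers = [1/λ − S/(1 − S)] × 365: (1.7247 − 1.2727) × 365 = 165 days and (2.8037 − 2.3333) × 365 = 172 days. The difference is 6.7 days.
- SDs are 104.5 and 105.0 days, so SE = √(104.5²/59.4 + 105.0²/40.5) = 21.4 and 6.7/21.4 = 0.31. Two-sided power = Φ(0.31 − 1.96) + Φ(−0.31 − 1.96) ≈ 6%.
- Log-rank on the same children: Φ(√99.9 × 0.4859/2 − 1.96) = Φ(0.47) = 68%.

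Simulation agrees:

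| Result | Share of trials |
|---|---|
| Table 20-type test rejects | about 5-6% |
| Log-rank rejects | about 67% (64% with 15% dropout) |
| Log-rank significant, Table 20 not | about 60-64% |
| Mean relapse time among relapsers shorter on tacrolimus, despite HR 0.615 | 37% |

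**(b) Relapse frequency.** The 15% loss is the plan's figure. The split by arm and the dispersion are assumptions. With equal true rates:

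| Dropout by arm | Wilcoxon on raw counts | Negative binomial with offset |
|---|---|---|
| 15% / 15% | 4.5-5.2% | 4.4-4.9% |
| 10% / 20% | about 6-7% | 5.5-6.1% |
| 10% / 30% | about 8-12% | 5.3-5.6% |

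At a rate ratio of 0.58 (zero-relapse probabilities 0.56 and 0.70) with 15% dropout in both arms, power is 70% for Wilcoxon and 78% for negative binomial.

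**(c) Steroid totals.** Take midpoints of the scheme in SAP 5.2.1 and no relapse.

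- The per-kg part is 17.5 + 10.5 + 7.875 + 5.25 + 2.625 = 43.75 mg/kg, or 962.5 mg for an assumed 22 kg child.
- The fixed part is 252 days × 1.25 mg = 315 mg. The per-kg share is 962.5/1277.5 = 75%.
- With weight log-SD 0.2-0.6 and remission 7-28 days after relapse (assumed), raw mg needs 1.2-3.5 times the sample size of mg/kg.
- In the base case (log-SD 0.4, 14 days), power in raw mg against mg/kg is 38% against 56% by Wilcoxon and 41% against 72% by t-test.

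The handling of early leavers matters separately. If truncated totals are counted and true dosing is equal, raw mg rejects in about 5% of trials at 15% dropout in both arms, 9-11% at 10% versus 20%, and 21-29% at 10% versus 30%.

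**(d) Change scores.** Sample size relative to ANCOVA is 2/(1 + ρ): 1.11 at ρ = 0.8, 1.33 at 0.5 and 1.54 at 0.3 (ρ assumed).

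**The case against.** Much of the plan is sounder than SAP 8.1.4 suggests when read alone. Four stronger readings are tempting, and the documents do not support them.

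- **That the SAP has no survival method for secondary time-to-event outcomes.** Tables 21-22 specify log-rank and Cox, and shells are part of the plan. At six months, log-rank and chi-square each have about 43% power, so the method only needs naming.
- **That the test on relapse counts is invalid.** The documents give 15% loss overall and no split by arm. With equal loss, Wilcoxon holds its level. Visible inflation needs an assumed imbalance such as 10% versus 30%.
- **That unscaled steroid totals bias the comparison, or that steroid substitution is unhandled.** Randomization balances weight on average, so the cost is precision. SAP 5.1 gives glucocorticoid conversions; Tables 28-29 merely do not refer to them.
- **That missing data by arm would be hidden.** The Table 23 and 67 shells carry N (Missing) by arm at each visit shown, and Tables 1 and 3 report drop-out and completion by arm.

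Time to first relapse within one year also largely repeats the primary endpoint, so Table 19 would put the correct result first. That limits the harm from Table 20. It does not justify printing a second P-value that conditions on relapse.

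**Conclusion.** The Table 20 P-value is wrong as written, and this part rests on the plan's own 0.56 and 0.70, exponential relapse times and 135 per arm. The test has about 5-6% power against about 67% for log-rank, and the two would disagree, with Table 21 significant and Table 20 not, in about 60-64% of trials.

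Relapse frequency needs a table and a follow-up adjustment. The absence of a comparison table is a fact of the SAP, but the size of any error depends on an assumed dropout imbalance. Scaling the steroid totals and adjusting for baseline are gains in precision, sized under assumed weights, remission times and correlations. The omission of Visit 3 is a plain inconsistency with the flow chart.

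The changes should be made. A reader might infer that the primary result is compromised; it is not, because SAP 8.1.3 names its own log-rank and Cox analysis and censoring rules.

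**What to change.** 1. Delete the P-value from Table 20 and keep the table descriptive. State in SAP 8.1.4 that the log-rank/Cox analyses of Tables 21-22 govern time to first relapse and six-month relapse-free survival.
2. Add a relapse-frequency table with relapses, person-time and rate by arm, and a rate ratio with 95% CI from negative binomial regression with log follow-up time as offset. The offset assumes a roughly constant rate. If the rate doubles after month 3, the test still rejects in only 5.6% of null trials at 10% versus 30% dropout.
3. Report steroid totals also in prednisone-equivalent mg per kg of baseline weight, using the SAP 5.1 conversions. State how children who leave early enter Tables 28-29, and add a sensitivity analysis for those who leave at relapse. Do not substitute a dose summed over visit intervals among children still followed. The Table 1 note foresees withdrawal at the endpoint event, and such children leave before their relapse steroids are counted. In simulation a true difference of about 11-12 mg/kg shrinks to about 8 if 30% of relapses lead to withdrawal, and to about zero if all do.
4. Compare eGFR and similar measures by baseline-adjusted ANCOVA at each visit. This gains efficiency and corrects no error.
5. Restore Visit 3 in Tables 23 and 67 and the shells copied from them.

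The cost is SAP text, shells, and a little more modelling and programming. All inputs are already scheduled for collection. The changes should be fixed before outcome data are analysed.
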